2.4 Regulatory Status

This study may include devices, components and accessories that are post-market (completely through the Quality System and approved for commercial use in India), pre-market (investigational and not completely through the entirety of the Quality System or not in accordance with labeled indications in India), and in some cases a combination of a post-market devices, accessories or components and an investigational device, accessory or component. All activities will be considered investigational.

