6.1.4 Study Data Collection

All study scans will be performed to satisfy one or more aims of the study, as follows:

- 1) **Aim 1:** Perform iterative evaluations of the device (including features, accessories and components) to optimize device performance, assess feasibility of new features, and to perform testing in general support of product and technology development. Aim 1 is to perform evaluations necessary to enable scientists and engineers to establish appropriate design specifications; to optimize the device, accessories, and their various components; and to establish feasibility. Evaluations conducted using investigational devices; devices with regulatory clearance but have not met requirements for commercial release; and devices used off label are included within the scope of this study.
- 2) **Aim 2:** Perform activities to support design validation and/or to confirm user requirements and specifications have been met, as per design controls and other applicable requirements. This includes activities to test that human image quality and system features are acceptable for clinical use and that the system usability meets user needs.
- 3) **Aim 3:** Evaluate device complaints and analyze potential causes. Aim 3 is to reproduce and, when possible, determine root cause of non-safety related complaints (e.g. reports of degraded image quality) that can only be reproduced and investigated in vivo.

Comparator devices (a device used to compare ultrasound against another research device) may be used during the study scans for any aim. Information about the scan (including the resultant images/electronic files, scan aim, date, and relevant parameters of scanning) may be accessed for research purposes.

Study Staff will record information in source documentation about each study scan including:

- Study aim(s) satisfied
- Date of scanning
- Duration of scan exposure
- Device identification (including applicable software versions)
- Anatomical region(s) scanned
- Subject ID#

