8.1 Data Reporting

A Final Clinical Study Report will be prepared by the Sponsor. This report will contain a report of the primary endpoint, and results from all study data collection activities will be stored at the investigational site (but are not prospectively planned to be summarized as part of the final study report for this study). Data collected from study scans in this study may be used for other engineering activities outside of the clinical report for this study, including activities such as retrospective analyses, meta-analysis, and other activities authorized by GE.

The final clinical report will contain a report of subject disposition and listing of AE/SAE by description, severity, and device relatedness of and unexpected device issues not anticipated based on engineering optimization activities. A summary of device complaints and resolution will be included in the final clinical report for this study. Individual narratives for each SAE and unexpected device issue will be summarized as part of the final report.

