9.2 Adverse Event Definitions

Adverse Event (AE): any untoward medical occurrence, unintended disease or injury, or untoward clinical signs (including abnormal laboratory findings) in subjects, users or other persons, whether or not related to the investigational medical device [ISO 14155:2011 3.2]. This includes events related to the investigational device or the comparator and to the procedures involved. For users or other persons, this is restricted to events related to the investigational medical device.

Serious Adverse Event (SAE): an adverse event that led to death; led to a serious deterioration in the health of the subject, that either resulted in a life-threatening illness or injury, a permanent impairment of a body structure or a body function, or in-patient or prolonged hospitalization, or medical or surgical intervention to prevent life-threatening illness or injury or permanent impairment to body structure or a body function; or led to fetal distress, fetal death or a congenital abnormality or birth defect. Planned hospitalization for a pre-existing condition, or a procedure required by the protocol without serious deterioration in health, is not considered a SAE [ISO 14155:2011 3.37].

Anticipated: Any adverse event and/or reaction, the specificity or severity of which is consistent with the IRB approved informed consent, protocol, investigator brochure, or product labeling.

Adverse Device Effect (ADE): an adverse event related to the use of an investigational medical device [ISO 14155:2011 3.1]. This includes any adverse events resulting from insufficient or inadequate instructions for use, deployment, implantation, installation, or operation, or any malfunction of the investigational medical device. This includes any event that is a result of a user error or intentional misuse of the investigational device [ISO 14155:2011 3.43].

Serious Adverse Device Effect (SADE): an adverse device effect that has resulted in any of the consequences characteristic of a serious adverse event [ISO 14155:2011 3.36].

Unanticipated serious adverse device effect (USADE): a serious adverse device effect, which by its nature, incidence, severity, or outcome has not been identified in the current version of the risk analysis report [ISO 14155:2011 3.42].

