9.3 Monitoring and Recording AEs and USADEs

All adverse events (AE), including all serious adverse events (SAE) and Unanticipated Serious Adverse Device Effects (USADEs), are required to be collected, investigated, and documented during the study reporting period, as defined in the study procedure set forth in this protocol. For the purposes of AE reporting, enrolled subjects will be monitored for AEs during the time between entering the research scanning area at the site for their research scan and the time that they exit the research scanning area. Subjects will not be followed for any potential or existing AEs after leaving the research scanning area, with the exception of SAEs that occur during scanning, which will be followed to resolution.

Study Title: Development Of Medical Ultrasound Systems, Accessories, And

Components - GE Bangalore

Study Number: 110.08-2015-GES-0004

Any AEs will be recorded on the Adverse Event Case Report Form. Documentation will include:

- Description of Event
- Date of onset and resolution
- Severity (mild, moderate, or severe)
 - *Mild:* Symptom(s) barely noticeable to the subject or does not make the subject uncomfortable. The AE does not influence performance or functioning. Prescription drugs are not ordinarily needed for relief of symptom(s).
 - *Moderate:* Symptom(s) of a sufficient severity to make the subject uncomfortable. Performance of daily activities is influenced. Treatment of symptom(s) may be needed.
 - *Severe:* Symptom(s) of a sufficient severity to cause the subject severe discomfort. Treatment for symptom(s) may be given.
- Serious (yes/no)
- Causal relationship to investigational medical device? (not related, possibly related, or related)
 - *Not related:* The adverse event is reasonably expected to be related to (or caused by) a concurrent illness, effect of another device/drug or other cause, and is unlikely related to the investigational product.
 - *Possibly related:* The adverse event is reasonably expected to be related to the investigational product, and an alternative etiology is equally or less likely compared to the potential relationship to investigational product.
 - *Related:* There is a strong relationship to investigational product or recurs on re-challenge, and another etiology is unlikely or there is no other reasonable medical explanation for the event.
- Treatment given and/or action taken (procedure stopped/paused, withdrawn from study, or no action)

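### The only causality item listed in Section 9.3 concerns the investigational device, so the final report's device-relatedness listing cannot attribute events caused by a comparator or a study procedure

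*Protocol*

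**What the plan says.** Section 9.2 defines an adverse event broadly. It counts "whether or not related to the investigational medical device", and the definition continues: "This includes events related to the investigational device or the comparator and to the procedures involved". Three sources of harm are therefore named.

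Section 6.1.4 makes the comparator a real possibility in this study: "Comparator devices (a device used to compare ultrasound against another research device) may be used during the study scans for any aim".

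Section 9.3 lists what is documented for each AE. The only causality item is "Causal relationship to investigational medical device? (not related, possibly related, or related)". The *Not related* category starts "The adverse event is reasonably expected to be related to (or caused by) a concurrent illness, effect of another device/drug or other cause" and then adds a second condition, that a relation to the investigational product is unlikely. No item on the comparator or the procedure is listed.

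Section 8.1 promises a final report with a "listing of AE/SAE by description, severity, and device relatedness".

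Section 2.4, on a study that mixes marketed and pre-market devices, says: "All activities will be considered investigational". The protocol does not define the term investigational product that the Section 9.3 categories use.

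**The concern.** Section 9.2 recognises three sources of study-caused harm and the Section 9.3 scale rates one. A skin reaction to a comparator probe, or an event brought on by a Valsalva maneuver (Section 6.1.3), is harm that the study caused. On the scale as written it can end up in the same category as an illness the subject already had.

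The primary endpoint is a count of scans by type (Section 3.3.1), so the AE listing is the main place where the final report says anything about harm to subjects. Aim 1 is to optimise devices, and Section 2.6.3 says they are frequently upgraded or modified. A relatedness column that cannot separate the prototype, the comparator, the procedure and background illness serves neither subject protection nor the engineering purpose well.

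**Working it through.** No arithmetic decides this point. The check is to take each possible cause of an event through Sections 9.2, 9.3, 3.3.2 and 8.1.

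**Step 1: which code does each cause receive under Section 9.3?**

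| Cause of the event | An AE under 9.2? | Code under 9.3 |
|---|---|---|
| Investigational device alone | Yes | *Related* or *Possibly related* |
| Comparator alone, taken as another device | Yes | *Not related* (both conditions met) |
| Comparator alone, taken as investigational because of 2.4 | Yes | *Related* or *Possibly related*, with no item saying which device |
| Study maneuver alone | Yes | *Not related* (other cause) |
| Concurrent illness | Yes | *Not related* |

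Rows two, four and five share one code. Rows two and three are the same event with opposite codes, and the choice turns on a term the protocol leaves undefined.

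**Step 2: is there a code for every mixed case?** Suppose both probes were used in one scan, the comparator is the more likely cause, and the investigational device still cannot be called unlikely.
- *Not related* fails, because it requires the investigational product to be an unlikely cause.
- *Possibly related* fails, because it requires the alternative cause to be no more likely than the investigational product.
- *Related* fails, because it requires another cause to be unlikely or no other reasonable medical explanation to exist.

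No category fits, and scans that pair two devices are where this case would arise.

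**Step 3: do the counts change?** Section 3.3.2 reports AEs and SAEs by number and type, without a causality filter. Section 9.3 requires every AE to be recorded. Section 9.4 sends all SAEs to the Sponsor within 72 hours whatever their cause. The counts are therefore the same under every row of the table. Only the relatedness column of the Section 8.1 listing differs.

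**Step 4: can the device be recovered from other records?** The items listed in Section 9.3 are description, dates of onset and resolution, severity, seriousness, causality, treatment or action, and anticipated or not. None is a device identifier, and onset is a date only. Section 6.1.4 records for each scan the aim, date, duration, device identification with software versions, anatomical region and subject number. The structured link between the two records is subject and date. Section 6.1.3 allows up to five scans per subject per day, so one subject-date can match up to five scan records, and a scan with a comparator involves more than one device. By contrast, Section 9.5 asks for both date and time when a device complaint is reported.

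**The case against.** The strongest reply is that nothing is miscounted. A reader might infer that comparator injuries are misclassified in, or lost from, the safety endpoint. The documents do not support that: as Step 3 shows, the endpoint does not depend on causality and every AE is recorded. Nor do Sections 9.2 and 9.3 contradict each other. One says what counts as an AE; the other asks a narrower question, to which *Not related* is the true answer when another device alone was the cause. The adverse device effect definition in Section 9.2 has the same narrow scope, "an adverse event related to the use of an investigational medical device", so the item matches the category it feeds. All of this stands.

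A reader might also infer that any involvement of another device forces *Not related*. It does not, because the second condition must hold too. Some procedural events, such as those from user error with the investigational device, are adverse device effects by definition. This stands as well. But the second condition is met when the comparator is the sole cause, and it produces the uncoded mixed case in Step 2.

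On traceability, the AE form itself is not shown and the Section 9.3 list is not declared complete. The free-text description could name the device, the anatomical region may separate same-day scans, and SAEs receive narratives under Section 8.1. This weakens any claim that the device can never be identified. It does not answer the point that nothing listed requires the device or the onset time to be recorded.

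Finally, Section 4.1 plans no comparative safety analysis. That lowers the stakes, but the listing by device relatedness is still promised and should be interpretable.

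**Conclusion.** The point holds as a gap in attribution. As written, the relatedness column cannot separate harm caused by a comparator or a study procedure from background illness. The coding of comparator events depends on an undefined term, and one plausible mixed case has no code. The protocol's safety counts are not affected.

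The size cannot be stated. The protocol gives neither the number of scans with a comparator nor an expected number of AEs, so any proportion of events misattributed would be a guess. The only figure the documents support is that subject and date may leave up to five scan records to choose from. Section 9.1 expects serious or chronic injury in no subject and describes several of the listed risks as rare or remote, so few events of consequence are likely to be involved.

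The conclusion assumes that the AE form follows the Section 9.3 list and that comparators are used in at least some scans, as Section 6.1.4 permits. If the form already records the device and the onset time, the traceability part falls away and the causality part remains. The change is worth making: the weight is modest, but so is the cost, and attribution may not be recoverable after an event has been recorded without these items.

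**What to change.** In Section 9.3 and on the AE case report form:

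- State whether a comparator counts as the investigational product, and say how Section 2.4 bears on this.
- Replace the single causality item with three ratings on the same scale: investigational device, comparator device, study procedure.
- Restrict the reference to another device or drug under *Not related* to items not used in the study scan.
- Check that the categories cover the case where the comparator is the more likely cause but the investigational device is not unlikely.
- Add time of onset, and the identification and software version of the device or devices in use. Section 6.1.4 already has these identifiers recorded for each scan.

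In Section 8.1, list AEs by these three sources in place of a single device-relatedness column.

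The cost is a form revision, a few lines of protocol text and a few extra fields per AE.

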9.4 Reporting AEs and USADEs

All SAEs and USADEs will be documented as outlined above and reported in writing to the Sponsor within 72 hours of knowledge of the event. The Adverse Event Case Report Form [REDACTED]

[REDACTED] will also be submitted to the study Sponsor within 72 hours of knowledge of the event.

If the event resulted in the death of a subject, the event will be reported to the Sponsor within 24 hours of knowledge of the event.

The Sponsor Medical Monitor is the contact for SAEs and/or USADEs at the following E-mail: [REDACTED].

Additional follow-up information may be requested by the Sponsor. In addition, safety information may be shared with regulatory agencies and other participating sites, as required by applicable law and regulation. AEs and SAEs will be reported to the EC/IRB per their policy.

Study Title: Development Of Medical Ultrasound Systems, Accessories, And

Components - GE Bangalore

Study Number: 110.08-2015-GES-0004

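### Do the device-relatedness codes in Section 9.3 leave some adverse events without a code, so that the planned safety listing would be unsound?

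*Protocol*

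**What the plan says.** Section 9.3 lists the items to be documented for each adverse event. One is "Causal relationship to investigational medical device? (not related, possibly related, or related", and each value has a definition with joined conditions:

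- *Not related*: the event is reasonably expected to come from a concurrent illness, "effect of another device/drug or other cause, and is unlikely related to the investigational product".
- *Possibly related*: a device relationship is reasonably expected, and "an alternative etiology is equally or less likely compared to the potential relationship to investigational product".
- *Related*: there is a strong relationship or recurrence on re-challenge, and "another etiology is unlikely or there is no other reasonable medical explanation for the event".

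Section 8.1 says where the code is used: the final report contains a "listing of AE/SAE by description, severity, and device relatedness". It adds that "Individual narratives for each SAE and unexpected device issue will be summarized as part of the final report". Section 9.2 defines an adverse device effect as "an adverse event related to the use of an investigational medical device". Under Section 9.4, all SAEs and USADEs are "reported in writing to the Sponsor within 72 hours of knowledge of the event".

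A second item on the same form is whether the event was anticipated. Section 9.2 defines this by consistency with the consent form, protocol, investigator brochure or labeling. Section 9.3 defines it as previously observed and documented in a section on foreseeable events. No section has the title given there; the nearest is Section 9.1.

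**The concern.** A causality scale should give each event one value. Here the definitions use different yardsticks. *Possibly related* compares the device with the alternative. *Not related* and *Related* use a bare term, unlikely, with no threshold.

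Take skin irritation after gel contact, a risk listed in Section 9.1, in a subject whose existing skin condition is judged the likelier cause. The device is plausible, so it is not clearly unlikely. The alternative is more likely, so *Possibly related* seems barred. Two raters working in good faith could code this event differently.

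At stake would be the consistency of the relatedness listing. It matters most for non-serious events, because Section 8.1 plans no narrative for each of them. If ADE status were read off the code, that could be inconsistent too. The two definitions of anticipated raise a similar doubt about that field.

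**Working it through.** The plan gives no figure to reproduce. The check is whether the three definitions cover every case, and then where the code goes.

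**1. Coverage under a strict reading of unlikely**

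| Situation | Not related | Possibly related | Related |
|---|---|---|---|
| Other cause expected, device unlikely | yes | no | no |
| Device plausible, alternative more likely | no | no | no |
| Device expected, alternative equally or less likely | no | yes | only if the link is strong and the alternative unlikely |
| Strong device link, alternative unlikely | no | yes | yes |

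The second row has no code. The fourth row has two, because an unlikely alternative is also a less likely one. The scale is therefore loose at both ends.

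**2. How wide the gap is**

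Assume, for illustration only, a single alternative cause. Let *p* be the probability that the device caused the event, so the alternative has probability 1 − *p*. Let *u* be the largest *p* still called unlikely. The protocol gives no value for *u*.

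- *Possibly related* needs 1 − *p* ≤ *p*, that is *p* ≥ 0.5.
- *Not related* needs *p* ≤ *u*.
- The uncoded range is *u* < *p* < 0.5, with width 0.5 − *u*.

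Results:

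- *u* = 0.10: 0.10 to 0.50, width 0.50 − 0.10 = 0.40.
- *u* = 0.25: 0.25 to 0.50, width 0.50 − 0.25 = 0.25.
- unlikely read as less likely than the alternative (any *p* below 0.5): the range is empty.

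The gap therefore depends on how one word is read. The first limb of *Not related* already asks for another reasonably expected cause, so taking unlikely as its counterpart is an ordinary reading.

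**3. Where the code is used**

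- Primary endpoint (3.3.1), number and type of scans: not used.
- Safety endpoints (3.3.2), number and type of safety issues including AEs and SAEs, and of device complaints: no breakdown by relatedness is specified.
- Reporting to the Sponsor (9.4), 72 hours for SAEs and USADEs and 24 hours for deaths: not used. By the definitions in 9.2 a USADE is a SADE, and a SADE has the consequences of an SAE, so the SAE rule already covers it.
- SAE narratives (8.1): written for each SAE whatever its code.
- Tests or comparisons: none planned (3.1, 4.1).
- AE/SAE listing (8.1): used, as one of three attributes beside description and severity.

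**4. ADE and SADE status**

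Section 9.2 defines these terms without reference to the 9.3 code. It does not say whether a possible relationship counts, and Section 8.1 plans no ADE or SADE table.

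**5. Anticipated**

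An event listed in Section 9.1 is documented in the protocol, so it would ordinarily count as anticipated under 9.2 as well as 9.3. The definitions part mainly for events documented only elsewhere, for example in labeling. Section 8.1 does not list the flag among the contents of the report, and USADE status refers to the risk analysis report instead.

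**The case for a change.** The strongest case for a change is textual. Where the authors wanted a relative comparison they wrote one, in *Possibly related*. The bare unlikely in *Not related* may therefore be meant as absolute, and then the gap is real. Reading it relatively has a cost, because an event with a plausible device contribution is recorded as not related. Section 7.2 allows device operators to qualify through engineering or imaging physics experience, so clinical convention cannot be counted on to fill the gap if such staff do the coding. A wording change would need no new data.

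The ambiguity stands. What does not follow is an effect on a result. The field has three permitted values and no blank option, so nothing supports the idea that events would go uncoded. Section 11.1.1 provides for training on the case report forms and allows for completion guidelines, which is a suitable place to settle a coding boundary. The listing carries a description and severity, so a non-serious event is not represented by its code alone.

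Nor is there one evident correction. Widening *Possibly related* to any plausible device relation would close the lower gap but enlarge the overlap with *Related*, unless events meeting *Related* were carved out. Moving the boundary the other way would send the same events to *Not related*. Where that line falls is largely a convention for the sponsor to choose.

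**Conclusion.** No change to the plan is called for. Section 9.3 is loosely worded at its lower boundary and overlaps at its upper one, but followed as written it leaves the scan counts, AE and SAE totals, SAE narratives and reporting to the Sponsor intact. The effect is confined to one of three named attributes in a descriptive listing, mainly for non-serious events, and the number of such events may be zero. The differing definitions of anticipated, and the mis-titled reference that apparently means Section 9.1, are clerical.

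This rests on three assumptions: staff pick one of the three values for every event; no ADE or SADE tabulation is planned beyond what Section 8.1 describes; and the ethics committee's own reporting policy, which Section 9.4 relies on but the protocol does not reproduce, does not turn on this boundary. A sponsor revising the form instructions for other reasons could tidy the wording then.
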